For intervention patients, the Biofourmis mobile application, Biofourmis arm band, digital blood pressure monitor, and digital weight scale will be provided at no cost to participants in the intervention group for the duration of the study. Participants will be able to keep the Biofourmis mobile app access but will need to return the blood pressure monitor, weight scale, and Everion arm band following study completion.

No additional hospital visits or out of pocket expenses related to study participation will be incurred.

Community Health Workers

CHWs for this study aim will be paid study staff and no remuneration for study aim participation will be given.

For guidance, refer to the following Partners policies:

Recruitment of Research Subjects

<https://partnershealthcare-public.sharepoint.com/ClinicalResearch/Recruitment%20Of%20Research%20Subjects.pdf>

Guidelines for Advertisements for Recruiting Subjects

<https://partnershealthcare-public.sharepoint.com/ClinicalResearch/Guidelines%20For%20Advertisements.1.11.pdf>

Remuneration for Research Subjects

<https://partnershealthcare-public.sharepoint.com/ClinicalResearch/Remuneration%20for%20Research%20Subjects.pdf>

CONSENT PROCEDURES

Explain in detail how, when, where, and by whom consent is obtained, and the timing of consent (i.e., how long subjects will be given to consider participation). For most studies involving more than minimal risk and all studies involving investigational drugs/devices, a licensed physician investigator must obtain informed consent. When subjects are to be enrolled from among the investigators' own patients, describe how the potential for coercion will be avoided.

Aim 1

Patients

After identifying eligible patients, a member of the study team will interview inpatients at the bedside or reach out to patients via phone to introduce the study. (For those patients interviewed as inpatients, a study team member will ask a member of the care team for permission to approach. After permission is obtained, eligible patients who are willing to speak to a research team member about the study aim will be approached by the care team.) A research team member will describe the nature of the study aim and expected involvement. If interested, the study coordinator will offer to give or send (via email or snail mail) the patient the study fact sheet. The fact sheet will distill the purpose and main components of the study aim in a simplified way so that patients can get an idea of what the study aim will involve by reading a single page. Involvement will include a qualitative interview, and chart review procedures. Patients contacted via phone will have an opportunity to have the info sheet sent to them (via email or snail mail), read about the process and procedures, ask questions, and engage in discussion about all study aim details. Patients will have time to read and review the information as well as ask questions or to have the coordinator call them via phone later if necessary.

If the potential participant is not interested and/or verbal consent is not obtained for participation, the patient will not be enrolled. If after hearing about the study aim and reviewing the study aim fact sheet, a potential participant is interested in participating in the study aim and meets all eligibility criteria, the patient will be verbally consented and be enrolled in the study aim.

Patients that are undecided on study aim participation may take additional time to consider enrollment and study coordinators may connect with patients up to three times via phone to clarify any outstanding questions prior to enrollment.

Patients that are interested will be verbally consented prior to being enrolled and complete the qualitative interview while in patient or via phone.

The interview will be conducted by the PI and a study coordinator via phone or at the patient's bedside and this will last for 25-minutes. All interviews will be recorded prior to verbatim transcription via TranscribeMe.

All patients may keep paper copies of the study aim fact sheet for future reference.

Community Health Workers

CHWs (n=20) working in MGH inpatient and outpatient settings will be identified for one of two focus groups (n=10/focus group) lasting 1.5 hours each. All CHWs will have experience providing direct care for HF patients. MGH CHWs will be emailed an informational letter and introduced to the study at CHW weekly departmental meetings. CHWs interested in participating will be verbally consented, enrolled and scheduled for a focus group at MGH ([name]), via virtual meeting accessed via MGB generated Zoom link, or at 1-2 MGH community clinics.

Aim 2

After identifying eligible patients contacted by Research Invitation, or by MGH primary care provider/cardiologist referral, a member of the study team will introduce the study. If interested in enrollment after hearing about the study, these

patients will have the option to complete all enrollment procedures and receive all equipment and study instructions by returning to MGH at a convenient time. Patients will have an opportunity to ask questions and engage in discussion about CHWs care delivery, the use of a Biofourmis mobile application, Everion, digital blood pressure monitor, digital weight scale, and all study aim details. Patients will have time to ask questions or to have the coordinator call back later via phone if necessary.

If the potential participant is not interested and/or consent is not obtained for participation, the patient will not be enrolled. If after hearing about the study aim, reviewing the study aim fact sheet and consent form, a potential participant is interested in participating in the study aim and meets all eligibility criteria, the patient may sign the consent form and be enrolled in the study aim.

Patients that are undecided on study aim participation may take additional time to consider enrollment up to 6 weeks or 3 study coordinator contacts after study coordinator initial contact; or up to 6 weeks after patients express interest via research invitation, or referral contact).

Patients that are interested will sign a consent form. Informed consent will be obtained by a clinical research coordinator or an MD. Capacity to consent will always be assessed by the Licensed Physician Investigator.

Enrolled participants will then meet their paired CHW, establish a plan for contact and a plan to reach patient-established goals. Enrolled participants will also be taught how to use the Biofourmis mobile application which will be uploaded to their phone. Enrollees will also be given and taught how to use the Everion, digital weight scale, and the digital blood pressure monitor. All participants will continue to engage with their CHW and be instructed on how to use the Biofourmis app and all hardware with opportunities to ask questions. Enrolled participants will also benefit from supervised practice of hard/software use. The expectation is that participants will have an established contact plan with their assigned CHW and be expert users of the Biofourmis platform.

All patients may keep paper copies of the study aim fact sheet and consent for future reference.

The CHWs participating in Aim 2 are paid members of the research study team.

Aim 3:

After identifying eligible patients contacted in the inpatient setting, by Research Invitation, or by MGH primary care provider/cardiologist referral, a member of the study team will introduce the study. If interested in enrollment after hearing about the study, these patients will have the option to complete all enrollment procedures and receive all equipment and study instructions by returning to MGH at a convenient time.

Patients will have an opportunity to ask questions and engage in discussion about CHWs care delivery, the use of a Biofourmis mobile application, Everion, digital blood pressure monitor, digital weight scale, and all study aim details. Patients will have time to ask questions or to have the coordinator call back later via phone if necessary.

If the potential participant is not interested and/or consent is not obtained for participation, the patient will not be enrolled. If after hearing about the study aim, reviewing the study aim fact sheet and consent form, a potential participant is interested in participating in the study aim and meets all eligibility criteria, the patient may sign the consent form and be enrolled in the study aim.

Patients that are undecided on study aim participation may take additional time to consider enrollment up to 6 weeks or 3 study coordinator contacts after study coordinator initial contact; or up to 6 weeks after patients express interest via research invitation, or referral contact).

Patients that are interested will sign a consent form. Informed consent will be obtained by a clinical research coordinator or an MD. Capacity to consent will always be assessed by the Licensed Physician Investigator.

Enrolled participants will then meet their paired CHW, establish a plan for contact and a plan to reach patient-established goals. Enrolled participants will also be taught how to use the Biofourmis mobile application which will be uploaded to their phone. Enrollees will also be given and taught how to use the Everion, digital weight scale, and the digital blood pressure monitor. All participants will continue to engage with their CHW and be instructed on how to use the Biofourmis app and all hardware with opportunities to ask questions. Enrolled participants will also benefit from supervised practice of hard/software use. The expectation is that participants will have an established contact plan with their assigned CHW and be expert users of the Biofourmis platform.

All patients may keep paper copies of the study aim fact sheet and consent for future reference.

The CHWs participating in Aim 3 are paid members of the research study team.

NOTE: When subjects are unable to give consent due to age (minors) or impaired decision-making capacity, complete the forms for Research Involving Children as Subjects of Research and/or Research Involving Individuals with Impaired Decision-making Capacity, available on the New Submissions page on the PHRC website:

<https://partnershealthcare.sharepoint.com/sites/phrmApply/aieipa/irb>

For guidance, refer to the following Partners policy:

Informed Consent of Research Subjects:

[https://partnershealthcare-public.sharepoint.com/ClinicalResearch/Informed Consent of Research Subjects.pdf](https://partnershealthcare-public.sharepoint.com/ClinicalResearch/Informed%20Consent%20of%20Research%20Subjects.pdf)

DATA AND SAFETY MONITORING

Describe the plan for monitoring the data to ensure the safety of subjects. The plan should include a brief description of (1) the safety and/or efficacy data that will be reviewed; (2) the planned frequency of review; and (3) who will be responsible for this review and for determining whether the research should be altered or stopped. Include a brief description of any stopping rules for the study, when appropriate. Depending upon the risk, size and complexity of the study, the investigator, an expert group, an independent Data and Safety Monitoring Board (DSMB) or others might be assigned primary responsibility for this monitoring activity.

NOTE: Regardless of data and safety monitoring plans by the sponsor or others, the principal investigator is ultimately responsible for protecting the rights, safety, and welfare of subjects under his/her care.

In addition to weekly data monitoring by the PI, a Data Safety Monitoring Board has been assembled that includes a NIH funded clinical trialist, a senior biostatistician and a NIH funded trialist and senior scientist that will meet annually to review all data and analysis, discuss progress, and challenges. All complaints about the study will be reviewed by the DSMB. The study may be stopped at any time if a safety or efficacy compromise occurs.

Describe the plan to be followed by the Principal Investigator/study staff for review of adverse events experienced by subjects under his/her care, and when applicable, for review of sponsor safety reports and DSMB reports. Describe the plan for reporting adverse events to the sponsor and the Partners' IRB and, when applicable, for submitting sponsor safety reports and DSMB reports to the Partners' IRBs. When the investigator is also the sponsor of the IND/IDE, include the plan for reporting of adverse events to the FDA and, when applicable, to investigators at other sites.

NOTE: In addition to the adverse event reporting requirements of the sponsor, the principal investigator must follow the Partners Human Research Committee guidelines for Adverse Event Reporting

Data review and database review will be completed by the PI, [name] each week to ensure the validity and integrity of the data generated in accordance with all study procedures described in the IRB-approved protocol. Progress reports based on data review and database review will be completed and sent to the DSMB quarterly to ensure that all procedures and data collection are in compliance with details specified in the IRB protocol. All adverse events will be reported to the IRB directly by the PI.

MONITORING AND QUALITY ASSURANCE

Describe the plan to be followed by the principal investigator/study staff to monitor and assure the validity and integrity of the data and adherence to the IRB-approved protocol. Specify who will be responsible for monitoring, and the planned frequency of monitoring. For example, specify who will review the accuracy and completeness of case report form entries, source documents, and informed consent.

NOTE: Regardless of monitoring plans by the sponsor or others, the principal investigator is ultimately responsible for ensuring that the study is conducted at his/her investigative site in accordance with the IRB-approved protocol, and applicable regulations and requirements of the IRB.

Data review and database review will be completed by the PI, [name] each week to ensure the validity and integrity of the data generated in accordance with all study procedures described in the IRB-approved protocol.

For guidance, refer to the following Partners policies:

Data and Safety Monitoring Plans and Quality Assurance

[https://partnershealthcare-](https://partnershealthcare-public.sharepoint.com/ClinicalResearch/DSMP_in_Human_Subjects_Research.pdf)

[public.sharepoint.com/ClinicalResearch/DSMP_in_Human_Subjects_Research.pdf](https://partnershealthcare-public.sharepoint.com/ClinicalResearch/DSMP_in_Human_Subjects_Research.pdf)

Reporting Unanticipated Problems (including Adverse Events)

[https://partnershealthcare-](https://partnershealthcare-public.sharepoint.com/ClinicalResearch/Reporting_Unanticipated_Problems_including_Adverse_Events.pdf)

[public.sharepoint.com/ClinicalResearch/Reporting_Unanticipated_Problems_including_Adverse_Events.pdf](https://partnershealthcare-public.sharepoint.com/ClinicalResearch/Reporting_Unanticipated_Problems_including_Adverse_Events.pdf)

PRIVACY AND CONFIDENTIALITY

Describe methods used to protect the privacy of subjects and maintain confidentiality of data collected. This typically includes such practices as substituting codes for names and/or medical record numbers; removing face sheets or other identifiers from completed surveys/questionnaires; proper disposal of printed computer data; limited access to study data; use of password-protected computer databases; training for research staff on the importance of confidentiality of data, and storing research records in a secure location.

NOTE: Additional measures, such as obtaining a Certificate of Confidentiality, should be considered and are strongly encouraged when the research involves the collection of sensitive data, such as sexual, criminal or illegal behaviors.

Privacy of study participants will be protected in the following ways. All patient information for the study will be stored in a locked study coordinator office at MGH. All medical records pertaining to the study that are no longer needed will be placed in HIPPA-compliant bins at MGH. All research team members for this study are CITI-certified and have a strong understanding of GCP.

All information and data concerning subjects or their participation in this study will be considered confidential. Only authorized personnel involved in the study will have access to these confidential files.

The electronic database generated will be password-protected and accessed only by authorized study staff trained on the importance of data confidentiality and record security (limited to the PI, co-investigators and statistical lead). There are no foreseen risks to privacy and all study participants will be assigned a unique study identification number as part of a Partners password protected REDCap database. Only de-identified data will be analyzed and published.

SENDING SPECIMENS/DATA TO RESEARCH COLLABORATORS OUTSIDE PARTNERS

Specimens or data collected by Partners investigators will be sent to research collaborators outside Partners, indicate to whom specimens/data will be sent, what information will be sent, and whether the specimens/data will contain identifiers that could be used by the outside collaborators to link the specimens/data to individual subjects.

No data will be sent to research collaborators outside Partners. The PI and co-investigators will have access to de-identified data solely for the purposes of routine data discussions contributing to the success of the study. Only de-identified data will be analyzed and published.

Specifically address whether specimens/data will be stored at collaborating sites outside Partners for future use not described in the protocol. Include whether subjects can withdraw their specimens/data, and how they would do so. When appropriate, submit documentation of IRB approval from the recipient institution.

RECEIVING SPECIMENS/DATA FROM RESEARCH COLLABORATORS OUTSIDE PARTNERS

When specimens or data collected by research collaborators outside Partners will be sent to Partners investigators, indicate from where the specimens/data will be obtained and whether the specimens/data will contain identifiers that could be used by Partners investigators to link the specimens/data to individual subjects. When appropriate, submit documentation of IRB approval and a copy of the IRB-approved consent form from the institution where the specimens/data were collected.

No data will be sent to research collaborators outside Partners. The PI and co-investigators will have access to de-identified data solely for the purposes of routine data discussions contributing to the success of the study. Only de-identified data will be analyzed and published.

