In Aim 3, we will conduct a randomized controlled trial among 50 patients with heart failure. Twenty-five patients (n=25) will be randomized to the digitally-enabled CHW intervention + usual care (explored in Aim 2) and 25 patients will be randomized to CHW care + usual care. Outcomes will include patient acceptability (defined by patient satisfaction, willingness to engage in the intervention again, etc.), feasibility (rate of patient biosensor, mobile application, symptom assessment, Everion sensor, digital blood pressure monitor, digital weight scale, and CHW interaction use) and preliminary effectiveness (30-day readmissions, ED visits, missed primary care and cardiology appointments). CHW exit interviews (15-minute) will also be conducted after each patient study interval ends. The hypothesis is that a 30-day digitally-enabled CHW intervention can generate high acceptability, feasibility, and preliminary effectiveness among patients with heart failure.

Aim1

Identification of 30 patient and 20 community health worker perspectives on barriers to heart failure care through semi-structured interviews and focus groups

Outcomes: The domains of the interview and focus group guides: HF knowledge, social (e.g., socioeconomic status, social support, living situations), behavioral (e.g., diet, activity), clinical (e.g., medication reconciliation, care plan adherence), communication-based (e.g., connection to care teams), digital (e.g., medication reminders, appointment reminders), human (e.g., CHW home visits, accompaniment to clinic visits), disease-based (e.g., HF and other comorbidities), cultural (e.g., health beliefs), or environmental (e.g., work, home) factors

Hypothesis: Interviews with patients with HF and CHW focus groups can improve a HF intervention

Aim 2

Conduct a 30-day open pilot trial with 30 patients (10 patients at a time for 3 consecutive cycles) at hospital discharge by orienting patients to the use of the digital platform and pairing patients with community health workers trained to use the digital platform and care for patients with heart failure.

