After completing the enrollment questionnaire, participants randomized to the digitally-enabled intervention arm will be given the Everion biosensor and digital weight scale and blood pressure cuff. Participants will be instructed to wear the Everion biosensor on their non-dominant arm and how it will track several body metrics including heart rate, oxygenation and activity levels. A study team member will guide the participant through downloading the Biofourmis app, and setup of the Biofourmis app as well as demonstrating all features. Patients will be instructed on how to use the digital weight scale and digital blood pressure cuff as well as the Biofourmis app. The Everion biosensor, digital weight scale and digital blood pressure monitor will be linked to the Biofourmis mobile phone application. To promote privacy of health information, a login will be required for access to app and all mobile phones will be set to password protected mode/touch ID activated (if not already).

For participants randomized to the intervention, at the time of enrollment, application permissions will be given. For the Biofourmis application to access any information on an iOS/Android smartphone, the application must ask the user for permission and only if that permission is granted, can the application access that information. This is inherently enforced on all applications by the operating system. In our case, we only will ask for permissions to access:

- Relevant digital-health data from Biofourmis platform physical/metabolic activity metrics including heart rate, oxygenation and activity levels
- Display notifications
- All clinical support team notifications

Participants randomized to the intervention arm will be advised that they will need to return the Everion device, digital weight scale and digital blood pressure monitor after the 30-day enrollment period ends. They will be advised that the app can be used freely after the study is concluded.

Participants will complete an enrollment questionnaire at the time of enrollment. A chart review will also be completed by study coordinators. Participants will be asked whether they own a home weight scale and blood pressure cuff. The study team will also assess the level of adherence based on self-reported symptom data collected in questionnaires as well as the Quality of Life Questionnaire and exit questionnaire administered on day 25 and day 30 after enrollment.

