Patient participants will complete exit interviews in-person or via phone after the 30-day study interval ends. Patient participants will be contacted by phone on day 25 and within 3 days of completing the 30-day intervention and exit interviews (25 minutes in length) will be scheduled either in-person (at MGH, [name]) or via phone. CHW study staff will also complete exit interviews in-person 3-5 days after each 30-day patient participant intervention ends.

All interviews will be audio recorded and transcribed verbatim. Interviews will be performed by the PI and a study coordinator trained in semi-structured interview administration. Expected completion of each iteration of 10 exit interviews will occur within 2 weeks of participants completing the 30-day intervention.

Patients that are admitted within 30 days of hospital discharge will be approached during their hospital admission to complete a short readmission questionnaire (10 minutes). An admission chart review will also be completed prior to discharge.

In addition, when patients are offered or trained in the intervention but decline to participate, reasons for non-participation will be assessed to inform enrollment barriers.

When the study arm ends or a participant's participation ends prematurely, those participants may keep their app (in which case their use will continue to be tracked), but will be asked to return the Everion device, the digital weight scale, and digital blood pressure monitor.

For studies involving treatment or diagnosis, provide information about standard of care at Partners (e.g., BWH, MGH) and indicate how the study procedures differ from standard care. Provide information on available alternative treatments, procedures, or methods of diagnosis.

Aim 1

This aim does not involve diagnostic processes. This use of qualitative interviews which may improve patient engagement and favorably effect outcomes including reduced rates of hospital readmission, ED visits, improved medication compliance and improved care plan adherence.

This Aim will complete the following in addition to standard of care:

- 1) Completion of qualitative interviews with patients
- 2) Completion of focus groups with community health workers

Aim 2

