Participants will continue to receive usual healthcare from their physicians along with CHW and digital platform support. While minimal safety risk is expected, this study aim is not designed to detract from or interfere with clinical care. Individuals unable or unwilling to participate in questionnaires, CHW interactions, mobile application or arm band wear or interviews will be withdrawn from the study aim. Study aim records that identify subjects will be kept confidential as required by law. Subject data will be de-identified in study aim records disclosed among MGH study co-investigators. Subjects will be encouraged to limit personal identifiers they enter into mobile applications.

Aim 3

Participants will continue to receive usual healthcare from their physicians along with CHW and digital platform support. While minimal safety risk is expected, this study aim is not designed to detract from or interfere with clinical care. Individuals unable or unwilling to participate in questionnaires, CHW interactions, mobile application or arm band wear or interviews will be withdrawn from the study aim. Study aim records that identify subjects will be kept confidential as required by law.

Subject data will be de-identified in study aim records disclosed among MGH study co-investigators. Subjects will be encouraged to limit personal identifiers they enter into mobile applications.

FORESEEABLE RISKS AND DISCOMFORTS

Provide a brief description of any foreseeable risks and discomforts to subjects. Include those related to drugs/devices/procedures being studied and/or administered/Performed solely for research purposes. In addition, include psychosocial risks, and risks related to privacy and confidentiality. When applicable, describe risks to a developing fetus or nursing infant.

Aim 1

No drugs or biologic procedures will be administered. There are no foreseeable discomforts or psychosocial risks to subjects. If after consenting to the study, study participants are no longer interested in being included in the study or are unable to complete the study for any reason, they will be withdrawn from the study. If there are any questions that make study participants uncomfortable, they may skip these questions.

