No drugs or biologic procedures will be administered. There are no foreseeable discomforts or psychosocial risks to subjects. If after consenting to the study, study participants are no longer interested in being included in the study or are unable to complete the study for any reason, they will be withdrawn from the study. If there are any questions that make study participants uncomfortable, they may skip these questions.

To mitigate the risk to privacy and confidentiality, all study participants will be assigned a unique study identification number as part of a MGB password protected REDCap database. Only de-identified data will be analyzed and published. Data will only be assessable to authorized study staff including the PI, co-investigators, and statistical staff.

In terms of device or mobile application use for participants randomized to the intervention arm, the following processes will mitigate the risk to privacy and confidentiality.

- A login will also be required for access to the Biofourmis application and the smart phone will be set to password protected mode / touch ID activated. At the time of enrollment, app permissions will be given.
- For an application to access any information on an iOS/Android smartphone, the application must ask the user for permission and only if that permission is granted, can the application access that information. This is inherently enforced on all applications by the operating system.
- In our case we only will ask for permissions to access:
 - Relevant digital-health data from Biofourmis platform including physical/metabolic activity metrics including heart rate
 - Display notifications
 - All clinical support team notifications

Any mobile app that is downloaded carries potential security risks and while a guarantee that this mobile application is risk free cannot be made, every effort has been taken to ensure that risk has been mitigated as listed above. In addition, weekly monitoring by the PI, [name] will occur to help identify and prevent any security issues.

In terms of all participants including those randomized to the control arm, the following processes will mitigate the risk to privacy and confidentiality:

- A login will be required for access to all REDCap questionnaire and chart review data.
- A login will be required for access to all Dedoose transcriptions and analysis

EXPECTED BENEFITS

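### Aim 3's withdrawal rules can lose acceptability ratings from people who refuse the intervention, and section 4.4 names no analysis set or denominator for the feasibility rates

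*Combined protocol and SAP*

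**What the plan says.** **Withdrawal.** Under the prompt on subject safety and objective drop criteria, the Aim 3 text says individuals "unable or unwilling to participate in questionnaires, CHW interactions, mobile application or arm band wear or interviews will be withdrawn from the study aim". Under Foreseeable Risks and Discomforts, the Aim 3 text adds that participants who lose interest or "are unable to complete the study for any reason, they will be withdrawn from the study".

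**Outcomes.** Specific Aims, Aim 3, lists "patient acceptability (defined by patient satisfaction, willingness to engage in the intervention again, etc".) and "feasibility (rate of patient biosensor, mobile application, symptom assessment, Everion sensor, digital blood pressure monitor, digital weight scale, and CHW interaction use"), alongside preliminary effectiveness.

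**Exit data.** The Aim 3 study procedures describe a Quality of Life Questionnaire and an "exit questionnaire administered on day 25 and day 30 after enrollment". They also say that every patient participant has a short exit interview with a questionnaire, face to face or by telephone, at day 25 and when the 30 days are up. The full questionnaire schedule is in supplemental documents that I have not seen.

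**After an early end.** "participants may keep their app (in which case their use will continue to be tracked), but will be asked to return the Everion device"; the scale and blood pressure monitor go back too. Chart review is planned for all participants.

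**Refusals.** "when patients are offered or trained in the intervention but decline to participate, reasons for non-participation will be assessed to inform enrollment barriers". This can reach people already enrolled, because training comes after enrolment: "Enrolled participants will also be taught how to use the Biofourmis mobile application which will be uploaded to their phone".

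**Analysis.** Section 4.4 promises summary statistics with 95% confidence intervals for acceptability and feasibility, and a summary of the activity log and use data. It names no analysis set, no patient or day denominator, and no handling of withdrawn participants. It expects loss to follow-up close to the under-3% seen in a previous CHW trial.

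**The concern.** Refusing the app, the arm band or the CHW is a feasibility result, and here it is also a ground for removal. A rule that removes people according to the outcome being measured leaves a more engaged group behind. A confidence interval computed in that group does not show the shift.

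Two outcomes are exposed in different ways. For acceptability, someone withdrawn before day 25 may never be asked for a rating, and no choice of analysis set recovers a rating that was not collected. For feasibility, the data up to withdrawal exist, so everything depends on who and which days enter the denominator, and section 4.4 leaves that open.

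The devices are issued only to the intervention arm, so the app and arm band triggers can arise only there, and withdrawal may differ by arm. Acceptability and feasibility are stated Aim 3 outcomes, and the hypothesis is that both will be high.

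**Working it through.** The plan gives no withdrawal count, use rate or satisfaction rate to reproduce. Its one Aim 3 design figure, at least 83% power, does not bear on this point. From the documents I take 25 per arm, 30 days and the under-3% loss figure. Withdrawal counts k = 1, 3, 5 and all rates below are assumptions.

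**Overlap of triggers and outcome.** The biosensor arm band, the app and CHW interaction appear in both lists. The blood pressure monitor and scale are feasibility components but are not named as triggers. The overlap is large, not complete.

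**Acceptability.** If x of (25 - k) raters are satisfied, the proportion over all 25 lies between x/25 and (x + k)/25, a band of width k/25.

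| k missing | Among raters | Over all 25 | Width |
|---|---|---|---|
| 1 | 19/24 = 79.2% | 76-80% | 4 points |
| 3 | 18/22 = 81.8% | 72-84% | 12 points |
| 5 | 16/20 = 80.0% | 64-84% | 20 points |

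Direction: in the last row, if 4 of the 5 non-raters would have been satisfied, the overall figure is 20/25 = 80%, unchanged. Fewer than 4 means the observed 80% overstates; all 5 means it understates.

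Share due to the rule: people who refuse questionnaires or withdraw consent give no rating under any rule. If m of the k would have been missing anyway, the rule accounts for (k - m)/25. With k = 5 and m = 3 that is 2/25 = 8 points. The widths in the table are therefore upper bounds.

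**Feasibility.** Assume 80% use among those retained, and withdrawn patients using the devices at that rate until day d and not after. Use over all 25 patients and 30 days is [(25 - k) × 0.80 + k × 0.80 × d/30] / 25.

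| k withdrawn | d = 0 (never used) | d = 15 |
|---|---|---|
| 1 | 76.8% | 78.4% |
| 3 | 70.4% | 75.2% |
| 5 | 64.0% | 72.0% |

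At 3% withdrawn: 0.97 × 0.80 = 77.6% for d = 0, and 77.6% + 0.03 × 0.40 = 78.8% for d = 15.

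**How much the denominator matters.** Take arm band days with 5 withdrawn on day 7 after 5 days of wear, and 20 retained wearing it 24 of 30 days. Days worn: 20 × 24 + 5 × 5 = 505.
- Retained patients only: 480/600 = 80.0%
- All 25, each over own days on study: 505/(600 + 35) = 79.5%
- All 25 over 30 days: 505/750 = 67.3%

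All three are compatible with section 4.4 as written.

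**Yardstick.** The Wilson 95% interval for 20 of 25 is 60.9% to 91.1%, about 15 points either side of its centre. It applies to a yes/no measure per patient; for a mean share of days it is only a rough guide.

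**The case against.** The drop criteria answer an ethics-form prompt about removing subjects. They govern participation, repeat the Aim 2 sentence, and do not mention datasets. Exit interviews and questionnaires are stated for all patient participants, with a telephone option. Some ratings would be lost under any rule. Someone unable to complete may be ill or readmitted rather than dissatisfied, so the direction of bias is assumed. Every withdrawal count is assumed too: at the plan's own 3%, if it applied here, the feasibility shift is only 1.2-2.4 points. Counting days after disengagement as no use is a choice of estimand, not the correction of an error.

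Most of this stands, and it limits the point. What remains is that the universal exit questionnaire is not said to reach people already withdrawn, that the under-3% figure is not tied to this rule, and that the choice of estimand has not been made.

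Three stronger readings are tempting, and the documents support none of them:
- *Low use alone leads to withdrawal.* The trigger is being unable or unwilling to participate; no use threshold is given.
- *Withdrawn participants are excluded from the analysis.* Nothing says so. The feasibility concern rests on a missing denominator.
- *The comparison of readmissions, ED visits and missed appointments is biased.* That would require leaving withdrawn patients out, whereas chart review is planned for everyone.

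**Conclusion.** The point holds as a low-cost improvement, with medium confidence. The Aim 3 rules select on engagement, which is close to what feasibility measures. They can cost ratings from people who decline the intervention but would still answer questions. Acceptability is then probably overstated, by an amount bounded by 4, 12 or 20 points for 1, 3 or 5 missing ratings out of 25. Feasibility is overstated only if withdrawn patients or their later days leave the denominator: 80% among those retained then stands for 64-78% over all 25 with 1-5 withdrawn, or about 78-79% at 3%.

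In most of these scenarios sampling error with 25 patients is larger. The difference is that the planned interval reports sampling error and does not report this shift. The conclusion rests on assumed counts and rates, and on the inference that acceptability is measured at the exit contacts, which the plan implies but does not state. The unseen questionnaire schedule could settle part of it.

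**What to change.** **Drop criteria and Foreseeable Risks, Aim 3.** State that disengaging from the intervention does not end data collection, which ends only when the participant withdraws consent. This leaves the management of the intervention itself untouched.

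**Study procedures, Aim 3.** Record each disengagement with date, reason and arm, as a feasibility result. Apply the exit questionnaire already planned for all, and the planned chart review, to every randomised participant who has not withdrawn consent.

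**Section 4.4, Aim 3.**
- Analyse effectiveness in all randomised participants by assigned arm.
- Report use over all 25 randomised to the intervention, and also among those still participating. State how days after disengagement are counted, using tracked app data where the app was kept.
- Report the number of missing acceptability ratings per arm, with best-case and worst-case bounds.

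**Cost.** Wording changes in the protocol and section 4.4, and a few extra telephone contacts. Reported feasibility and acceptability may come out lower.
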